#### 5.2 Randomization

Participants will be randomized into one of three groups as shown below:

	Pre-op Package	Post-op Package
Pre-op group	ZNS 100 mg PO	Placebo
Placebo group	Placebo	Placebo
Post-op group	Placebo	ZNS 100 mg PO

Randomization will be based on a randomization list generated by unblinded statistician using a computer algorithm written in SAS using randomly selected blocks of sizes 3. Within each block of 3, there will be 1 subject assigned to each study group. To balance noise-exposure history across study arms we will employ stratified randomization. The subjects will be stratified based on noise exposure survey responses (see table below), and will then be randomized to study groups. The random assignment of subjects to the different study groups will be associated with consecutively assigned random numbers which will be unique for each study participant. The stratified kit list will be provided to Advanced Rx who will package and label the drug for shipment to the pharmacist. Each kit will contain two bottles and will be labeled with the same kit number. The bottle will not contain any information of the treatment allocation. One interim analysis is planned, once 33% (n=78) of the subjects have completed participation in the study.

Study medication will be dispensed to the participants with instruction to take their first assigned dose prior to surgery. Participants will take their second assigned dose within 12 hours after surgery or when the patient is released clinically to oral medication. Participants will be instructed to take zonisamide without food. We will recommend that capsules be swallowed whole per the current approved labeling.

Name	Description
1. High Noise	Screening: LENS-Q Adapted for Surgical Noise Study –

Name	Description
	a.Daily, Or b.Less than daily/more than weekly, Or c.Weekly, Or d.Less than weekly/more than monthly Or e.Monthly OR 1C Or 2C Or 3C >= 5 Years
2: Low Noise	Screening: LENS-Q Adapted for Surgical Noise Study –  1A AND 2A AND 4A = f.Less than monthly/more than yearly, g.Yearly, h.Less than yearly Or i.Never  OR  1C AND 2C AND 3C < 5 Years

## 5.3 Standard of Care Surgery

Patients will undergo a typical preoperative workup in preparation for surgery, including routine lab work, pregnancy testing (females only), and a preoperative assessment by anesthesiology. Patients will undergo their procedure per surgical protocol.

## 5.4 Intra-operative Testing

Documentation of drilling noise, as recorded by a probe mic in the contralateral ear to capture only ambient OR noise intensity level and duration from the non-operated ear during surgery. Documentation will also include duration of anesthesia.

## 5.5 Follow-Up Assessments

The follow-up assessments will occur after surgery and include the following tests or procedures:

- 1. DPOAE testing in recovery, within 8 hours after surgery.
- 2. Blood samples taken within 12 hours following the first pill for PGx surveys.
- 3. Collection of laboratory test results for research purposes that include an electrolyte panel, BUN, Cr, ALT, and AST. If these tests are not performed as part of clinical care post-operatively, we will obtain them for research purposes at the time of the PGx blood draw.
- 4. DPOAE, Audiogram, ECochG, and WIN testing 30 days (+/-3 days) after surgery.
- 5. Completion of the Hearing History and Occupation Exposure questionnaire 30 days (+/- 3 days) after surgery.
- 6. Documentation of adverse events.

Follow-up assessments will be planned at the stated time points; actual follow up times may vary due to patient logistics and compliance.

#### 5.6 Blood collection, transportation, and storage

Blood samples will be collected from each participant during the baseline visit and the post-surgery visit within 12 hours after the pre-operative drug dose. A post-operative nurse will draw blood into a red-top tube (EDTA or citrate) using an IV line. Samples will be labeled with a study identification number. They will be stored in a 2-8°C degree refrigerator at WUSM. Samples will then be transported weekly by a study team member for extraction and stored in a -80°C freezer at Gateway Biotechnology's lab.

#### 6.0 EVALUABILITY

All participants are evaluable for the primary outcome – the proportion of patients who are PTS positive as defined by the ratio of the number of participants with  $\geq 10$  dB increase in PTS to the total number of participants tested 30 days (+/- 3 days) post-surgery – provided they have had the assigned study dose and undergone the post-op study assessments.

Participants who receive the study medication are evaluable for toxicity related to the drug. Participants are evaluated from the time of dose administration through two weeks post dose for drug related adverse events.

The participant will be withdrawn from the study if:

- Participant withdraws consent
- Investigator removes the participant from study
- The Sponsor decides to close the study

#### 7.0 PHARMACEUTICAL INFORMATION

## 7.1 Zonisamide (ZONEGRAN®)

#### 7.1.1 Zonisamide Description

**Molecular formula:** C8H8N2O3S **Molecular weight:** 212.23

## 7.1.2 Clinical Pharmacology

The precise mechanism(s) by which ZNS exerts its antiseizure effect is unknown. ZNS may produce these effects through action at sodium and calcium channels. In vitro pharmacological studies suggest that ZNS blocks sodium channels and reduces voltage-dependent, transient inward currents (T-type Ca2+ currents), consequently stabilizing neuronal membranes and suppressing neuronal hypersynchronization. Additional information can be found in the package insert.

## 7.1.3 Supplier

ZNS will be supplied through Advanced Rx (Fort Washington, PA).

## 7.1.4 Dosage Form and Preparation

ZONEGRAN® is commercially available for oral administration as capsules containing 25 mg, 50 mg, or 100 mg of ZNS.

Each 100 mg capsule contains the labeled amount of ZNS plus the following inactive ingredients: microcrystalline cellulose, hydrogenated vegetable oil, gelatin, and titanium dioxide.

## 7.1.5 Storage and Stability

Store at 25°C (77°F), excursions permitted to 15–30°C (59–86°F), in a dry place and protected from light.

#### 7.1.6 Administration

For subjects randomized to "ZNS pre-op", the pre-op package will contain ZNS capsules (100 mg) and the post-op package will contain placebo capsules that look and taste the same as ZNS capsules. For subjects randomized to "ZNS post-op", the pre-op package will contain placebo and the post-op package will contain ZNS (100 mg). For the subjects randomized to "placebo", both pre- and post-op packages will contain placebo. Participants will be instructed to take zonisamide without food. We will recommend that capsules be swallowed whole per the current approved labeling.

#### 7.1.7 Side Effects

Potential side effects from the administration of ZNS:

- Somnolence
- Anorexia
- Dizziness
- Ataxia
- Agitation/irritability
- Difficulty with memory and/or concentration

ZNS may cause serious side effects, including:

- Serious skin rash that can cause death.
- Serious allergic reactions that may affect different parts of the body.
- Less sweating and increase in body temperature (fever).
- Suicidal thoughts or actions in some people.
- Increased level of acid in blood (metabolic acidosis).
- Problems with concentration, attention, memory, thinking, speech, or language.
- Blood cell changes such as reduced red and white blood cell counts.

#### 7.2 Placebo

The placebo will contain microcrystalline cellulose which is the predominant filler in the generic capsule.

## 8.0 REGULATORY AND REPORTING REQUIREMENTS

The entities providing oversight of safety and compliance with the protocol require reporting as outline below. Please refer to Appendix A for definitions and Appendix B for a grid of reporting timelines.

Adverse events will be tracked for the WU site from the time of dose administration through two weeks post dose and at the follow up 30 day visit for drug-related adverse events. All adverse events will be documented and assessed for relatedness to the study medication.

The study team will monitor for adverse events on an ongoing basis. Once the team becomes aware of an adverse event, the AE will be reported according to institutional guidelines. Reporting requirements for Washington University study team may be found in Section 8.1. Reporting requirements for secondary site study teams participating in Washington University-coordinated research may be found in Section 8.2.

In the event of a Serious Adverse Event determined by the PI to necessitate the breaking of the blind, the intervention assignment will be revealed by the independent programmer to the medical staff doctor caring for the patient. In the event the statistician is unable to be reached in a time needed, to assure the safety of the subject, the blind can be broken by [name] and information will be shared with the medical staff assuming care for the research subject.

#### **8.1 Sponsor-Investigator Reporting Requirements**

# 8.1.1 Reporting to the Human Research Protection Office (HRPO) at Washington University

Reporting will be conducted in accordance with Washington University IRB Policies.

Pre-approval of all protocol exceptions must be obtained prior to implementing the change

#### **8.1.2** Reporting to the FDA

The conduct of the study will comply with all FDA safety reporting requirements. It is the responsibility of the Washington University principal investigator to report to the FDA as follows:

- Report any unexpected fatal or life-threatening suspected adverse reaction (refer to Appendix A for definitions) no later than 7 calendar days after initial receipt of the information.
- Report a suspected adverse reaction that is both serious and unexpected (SUSAR, refer to Appendix A) no later than 15 calendar days after it is determined that the information qualifies for reporting. Report an adverse event (refer to Appendix A) as a suspected adverse reaction only if there is evidence to suggest a causal relationship between the drug and the adverse event, such as:
  - A single occurrence of an event that is uncommon and known to be strongly associated with drug exposure
  - One or more occurrences of an event that is not commonly associated with drug exposure but is otherwise uncommon in the population exposed to the drug

- An aggregate analysis of specific events observed in a clinical trial that indicates those events occur more frequently in the drug treatment group than in a concurrent or historical control group
- Report any findings from epidemiological studies, pooled analysis of multiple studies, or clinical studies that suggest a significant risk in humans exposed to the drug no later than **15 calendar days** after it is determined that the information qualifies for reporting.
- Report any findings from animal or in vitro testing that suggest significant risk in humans exposed to the drug no later than 15 calendar days after it is determined that the information qualifies for reporting.
- Report any clinically important increase in the rate of a serious suspected adverse reaction of that listed in the protocol or IB within 15 calendar days after it is determined that the information qualifies for reporting.

Submit each report as an IND safety report in a narrative format or on FDA Form 3500A or in an electronic format that FDA can process, review, and archive.

Each notification to FDA must bear prominent identification of its contents ("IND Safety Report") and must be transmitted to the review division in the Center for Drug Evaluation and Research (CDER) or in the Center for Biologics Evaluation and Research (CBER) that has responsibility for review of the IND. Relevant follow-up information to an IND safety report must be submitted as soon as the information is available and must be identified as such ("Follow-up IND Safety Report").

#### **8.1.3** Reporting to Secondary Sites

The Washington University Sponsor-Investigator will notify the research team at the secondary site of all unanticipated problems involving risks to participants or others that have occurred at other sites within 10 working days of the occurrence of the event or notification of the Sponsor-Investigator of the event. This includes events that take place both at Washington University and at other site, if applicable.

## 8.2 Secondary Site Reporting Requirements

The research team at each secondary site is required to promptly notify the Washington University Sponsor-Investigator of all serious adverse events (refer to Appendix A, Section D) within **1 working day** of the occurrence of the event or notification of the secondary site's PI of the event. This notification may take place

via email if there is not yet enough information for a formal written report (using FDA Form 3500a (MedWatch) and Washington University's cover sheet (Appendix C). A formal written report must be sent to the Washington University Sponsor-Investigator and designee within 4 calendar days (for fatal or lifethreatening suspected adverse reactions) or 11 calendar days (for serious unexpected suspected adverse reactions) of the occurrence of the event or notification of the secondary site's PI of the event.

The research team at the secondary site is responsible for following its site's guidelines for reporting applicable events to its site's IRB according to its own institutional guidelines. The research team at Washington University is responsible for reporting all applicable events to the FDA as needed.

Washington University pre-approval of all protocol exceptions must be obtained prior to implementing the change. Local IRB approval must be obtained as per local guidelines. Washington University IRB approval is not required for protocol exceptions occurring at secondary sites.

## 8.3 Exceptions to Expedited Reporting

Events that do not require expedited reporting as described in Section 1.1 include:

- planned hospitalizations
- hospitalizations < 24 hours
- respite care
- events related to disease progression

Events that do not require expedited reporting must still be captured in the EDC.

#### 9.0 STUDY CALENDAR

	Screening / Baseline	Surgery	Po	ost-op
	Within 30 days (+3 days) prior to surgery		Within 12 Hours	30 days (+/- 3 days)
Informed consent	X			
Clinical Exam	X			
Demographic Info	X			
Pre-Op Data (pregnancy test, lab results (electrolyte panel, BUN, Cr, ALT, and AST))	X			
Current Meds	X			
Questionnaire	X			X
Audiogram	X			X
ECochG	X			X
DPOAE	X		X*	X
WIN	X			X
Randomization	X			
Oral Dose**		X	X	
Blood draw***	X		X	
AE assessment		X	X	X

\* Within 8 hours

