#### 4.0 STUDY DESIGN

This study is a randomized, double-blinded placebo-control trial with three parallel groups, to make use of a common control group. Subjects will be randomized in a balanced fashion into one of 3 arms: ZNS 100 mg pre-op, Placebo, or ZNS 100 mg post-op.

The primary efficacy endpoint will be the proportion of PTS-positive subjects defined as the ratio of PTS-positive subjects to total number of subjects within each study arm/group. Subjects defined as PTS-positive will demonstrate an increase in threshold that is ≥10 dB HL at any frequency from 2-6 kHz post-surgery as compared to baseline audiogram.

The secondary efficacy outcome measures will be: (1) the proportion of PTS-positive subjects as defined above, but the definition of PTS will also include the NIOSH red

flag guideline for permanent threshold shift: an increase in hearing threshold level of 15 dB or more at any frequency (2, 3, 4, 6 kHz). (2) The rate of temporary cochlear change as measured by a DPOAE amplitude shift at any frequency that is significantly greater than the stability of each measurement (i.e., 95% confidence interval of each measurement do not overlap). The rate of DPOAE shift is the ratio of DPOAE shift-positive subjects to total subjects within each arm.

To ensure double-blinding of the trial, each subject will be randomized to one of three treatment arms via an interactive randomization tool (IRT) and assigned to study group. Once randomized, each subject will be provided a kit on the day of surgery that contains two bottles, with one package labeled to be taken prior to surgery and another package designated to be taken within 12 hours after surgery or when the patient is released clinically to oral medication. For subjects randomized to "ZNS pre-op", the pre-op package will contain one ZNS capsule (100 mg PO) and the post-op package will contain one placebo capsule that looks, smells, and tastes the same as ZNS capsules. For subjects randomized to "ZNS post-op", the pre-op package will contain one placebo capsule and the post-op package will contain one ZNS capsule (100 mg PO). For the subjects randomized to "placebo", both pre- and post-op packages will contain placebo.

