#### 12.0 STATISTICAL CONSIDERATIONS

## 12.1 Data Analysis

Data will be analyzed using an intention-to-treat principle with patients analyzed in the groups they were randomized to. The primary outcome measure for assessing effectiveness of ZNS (100 mg PO) pre-op will be the proportion of subjects in the pre-op arm experiencing PTS as compared to the control group. The primary outcome measure for assessing effectiveness of post-op ZNS (100 mg PO) will be the proportion of subjects in the "post-op" arm experiencing PTS as compared to the control group. The secondary outcome measures are key audiological and clinical assessments of hearing loss. OAE shift will be a secondary outcome measure and an early indicator of changes in cochlear health and PTS.

Standard descriptive statistics will be used to describe distribution of demographic, clinical and audiometric characteristics as well as outcome measures for each study group. For continuous level characteristics Q-Q plots and Shapiro-Wilk test will be used to test assumption of normality. For normally distributed data, mean and standard deviation will be used as descriptive stats of continuous level variables, and if the assumption of normality is violated we will report median and range for description of variables. Frequency and relative frequency will be used for description of categorical level variables.

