4.2 Intent-to-treat (ITT) sample

ITT sample will include all subjects who are randomized. Following principles of intent-to-treat analysis all subjects will be analyzed in the treatment group they were randomized to when they were enrolled in the study.

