5.2 Missing Data

Every attempt will be made to ensure data completeness. We do not anticipate much loss to follow-up because of the relatively short time follow-up interval. Conservatively, we would estimate that fewer than 5% of subjects will drop out/withdraw from the study. The subject will be withdrawn from the study follow-up and procedures if the subject withdraws consent, or the sponsor decides to close the study.

Data loss, if any, would almost likely be due to subjects refusing to complete or not returning at all for the post-surgery assessment of PTS 30 days (+/- 3 days). If the subject reschedules the post-surgery appointment for a later date for any reason, and if this delay is within 30 days of the

scheduled date, the data will be considered valid and used in the efficacy analysis. Any measure outside this time window of +30 days will be defined and considered as missing data.

Missing PTS at 30 days will be imputed using SAS PROC MI procedure within each treatment group using the distribution implied by the non-missing data for the specific treatment group. The SAS code below using Multiple Imputation by Chained Equations (MICE) via the Fully Conditional Specification (FCS) statement will be used to impute the missing data under the missing at random (MAR) assumption.

```
PROC MI DATA=X SEED=<value> NIMPUTE=10 OUT=MI_OUT1 NOPRINT;
CLASS GROUP;
VAR AGE PTA LSurg......;
FCS LOGISTIC(PTS);
RUN:
```

Each of the 10 complete data sets will be then analyzed using Fisher's exact test. One-sided p-value (p_i) from Fisher's exact test will be converted to a z-value using the inverse Normal transformation [1,2], i.e. $z_i = \Phi^{(-1)}(1-p_i)$, where $\Phi^{(-1)}(\cdot)$ represents the inverse standard Normal cumulative distribution function.

SAS funtion to convert Fisher's exact P-value to Z-value is as follows:

```
Z_i= QUANTILE('NORMAL', p_i, 0, 1);
```

The estimated z-vales from the 10 imputed datasets will be then combined following Rubin's rules using PROC MIANALYZE procedure in SAS which will be of the form:

```
PROC MIANALYZE DATA=Y;

MODELEFFECTS Z_i;

STDERR Z_i;

ODS OUTPUT ParameterEstimates=XX;

RUN:
```

The pooled estimate of z-vales from PROC MIANALYZE procedure will be then converted to probability value using the following SAS function:

```
P value=PROBNORM(estimate);
```

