 z_a = the $100(1-\alpha)^{th}$ percentile of the standard Normal distribution.

The proportion difference between groups is: $\mathbf{D} = \mathbf{p_1} - \mathbf{p_2}$

The lower (l_D) and the upper limits (u_D)of 100 (1- α)% confidence interval for D will be calculated as:

$$l_D = D - \sqrt{(p_1 - l_1)^2 + (u_2 - p_2)^2}$$

$$u_D = D + \sqrt{(p_2 - l_2)^2 + (u_1 - p_1)^2}$$

A supportive logistic regression analysis will be done with covariates: age, pre-op hearing dichotomized to normal to minimal hearing loss and slight to mild loss, noise exposure history dichotomized to high risk and low risk, exposure categorized as low (8-hour equivalent A-weighted sound level in decibel (LAeq8hr) < 80 dBA), moderate (LAeq8hr > 80 dBA but < 90 dBA), or high (LAeq8hr > 90 dBA).

```
PROC LOGISTIC DATA=X;
CLASS GROUP;
   MODEL PTS = COVARIATE1 COVARIATE2.. ;/*Covariates are as mentioned above*/
RUN;
```

Sensitivity analysis of the primary endpoint

The potential impact of missing primary endpoint data will be explored in sensitivity analyses using multiple imputation. Two sensitivity analyses performed:

Sensitivity 1: MI analysis under the missing not at random assumption (MNAR) Sensitivity 2: Logistic regression tipping point analysis under the assumption of data missing at random.

Sensitivity 1

Proc MI procedure in SAS will be used to impute missing data for study treatment groups using the distribution implied by the non-missing patient data within the placebo group. The SAS code to impute data for Sensitivity analysis 1 under the MNAR assumption will be of the form:

```
PROC MI DATA=X SEED=<value> NIMPUTE=10 OUT=MI_OUT1 NOPRINT;
CLASS GROUP;
VAR AGE PTA LSurg......;
FCS LOGISTIC(PTS);
RUN;
```

Post imputation each of the imputed 10 datasets will be analyzed using the same approach as for the primary outcome measure. The estimates of the analysis of the 10 imputed datasets will be then combined following Rubin's rules using PROC MIANALYZE procedure in SAS which will be of the form:

```
PROC MIANALYZE PARMS=GMPARMS COVB=GMCOVB PARMINFO=GMPINFO WCOV BCOV

TCOV; / *dataset "gmparms" contains the estimates and associated standard errors
for the mean parameters from each of the M=10 imputed data sets.
dataset "gmcovb" contains the asymptotic covariance matrics
dataset "gmpinfo" contains parameter info*/

MODELEFFECTS INTERCEPT AGE PTA LSurg......;
RUN;
```

Sensitivity 2

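### Randomisation is scheduled at the baseline visit, up to 33 days before the assignment is first used, so a subject whose operation is then cancelled stays in the ITT sample, and the documents conflict on how to count that subject.

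*Protocol*

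**What the plan says.** **Timing.** Protocol 9.0 and SAP 2.6 mark randomisation once, in the screening/baseline column, headed "Within 30 days (+3 days) prior to surgery". Protocol 4.0 puts first use of the assignment later: "Once randomized, each subject will be provided a kit on the day of surgery that contains two bottles". SAP 2.5 agrees. The first capsule is taken before surgery and the second "within 12 hours after surgery or when the patient is released clinically to oral medication" (Protocol 5.2). The stratum comes from a questionnaire completed at baseline.

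**Who is analysed.** Protocol 12.1: "Data will be analyzed using an intention-to-treat principle with patients analyzed in the groups they were randomized to". SAP 4.2: "ITT sample will include all subjects who are randomized". Neither sets a condition on dose, surgery or drilling.

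**Missing outcomes.** SAP 5.2: "Missing PTS at 30 days will be imputed using SAS PROC MI procedure within each treatment group". The first sensitivity analysis (SAP 7.1.1) imputes instead from the "distribution implied by the non-missing patient data within the placebo group". The missing-data sections of both documents foresee refusal and failure to attend. They do not mention cancelled surgery.

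**Passages that point the other way.** Protocol 6.0 treats participants as evaluable for the primary outcome "provided they have had the assigned study dose and undergone the post-op study assessments", and its denominator is those tested at 30 days. SAP 3.1 defines the estimand for adults who undergo drilling, and its 30-day clock starts at randomisation. SAP 4.4 limits the per-protocol sample to subjects treated in compliance.

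**The concern.** Early randomisation has no stated purpose here, because no listed activity needs the assignment before kit hand-over. It opens a gap of up to a month in which an elective operation can be cancelled, and entry requires only that the operation be planned. A patient lost in that gap has already used a randomised slot.

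Under the SAP that patient is then given a PTS result modelled on people who were drilled and dosed. The result describes an exposure that never happened, in a patient outside the estimand's own population.

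Two things are at stake. One is power, since 78 per arm contains no allowance for such losses. The other is a clear primary analysis, since the sections disagree on whether the patient counts.

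**Working it through.** **1. The gap.** The outer limit of the visit window is 30 + 3 = 33 days before surgery.

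**2. The plan's own power figure.** Inputs from Protocol 12.3: n = 78 per arm, PTS in 50% on placebo and 25% on ZNS, Fisher's exact test, one-sided alpha 0.0125.

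- Exact power is the sum, over all pairs (x₁, x₂), of Bin(x₁; 78, 0.50) × Bin(x₂; 78, 0.25), counting pairs whose one-sided hypergeometric p-value is ≤ 0.0125. Result: **80.7%**.
- The arcsine approximation with continuity correction is Φ(√(2n)·|A − B| − z). Here A = arcsin√(0.50 − 1/156) = 0.7790, B = arcsin√(0.25 + 1/156) = 0.5310, √156 = 12.490 and z = 2.241. This gives Φ(3.098 − 2.241) = **80.4%**, the stated figure.

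**3. Loss from subjects never operated on.** The documents give no cancellation rate, so the share c is an assumption. Per arm, m = 78(1 − c), rounded, and the exact formula is rerun with m. The last column is 234/(1 − c), rounded up: the number to randomise so that 234 are operated on.

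| c (assumed) | Operated per arm | Lost of 234 | Exact power | To randomise |
|---|---|---|---|---|
| 0% | 78 | 0 | 80.7% | 234 |
| 2% | 76 | 6 | 79.2% | 239 |
| 5% | 74 | 12 | 77.9% | 247 |
| 10% | 70 | 24 | 75.6% | 260 |
| 15% | 66 | 36 | 71.9% | 276 |

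These are powers from observed subjects. Imputation within arm under missing-at-random adds essentially no information about the treatment difference, so it does not recover the loss.

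**4. First sensitivity analysis.** As a rough approximation, placebo-based imputation moves the ZNS rate to 0.25(1 − c) + 0.50c. That is 0.2550, 0.2625, 0.2750 and 0.2875 for the four non-zero shares. Treating all 78 per arm as observed, exact power is 78.8%, 75.6%, 70.0% and 63.9%.

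**5. The same cancelled subject under each section.**

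| Section | Treatment of the subject |
|---|---|
| Protocol 12.1, SAP 4.2 | In, as randomised |
| SAP 5.2 | PTS imputed from the same arm |
| Protocol 6.0 | Not evaluable |
| SAP 3.1 | Outside the population (no drilling) |
| SAP 4.4 | Excluded from the per-protocol sample |

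**6. The estimand clock.** Thirty days ± 3 after randomisation is day 27 to day 33. For a subject randomised 33 days before surgery, that is 27 − 33 = −6 to 33 − 33 = 0 days relative to surgery. The estimand's time point then falls on or before the operation. The endpoint in SAP 3.2 is read 27 to 33 days after surgery, which for this subject is 60 to 66 days after randomisation.

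**The case against.** The strongest reply is that the effect cannot be sized from the documents and may be small. Their only loss figure is under 5% for drop-out or withdrawal (SAP 5.2); at 2% power is still 79.2%, and at 5% it is 77.9%. Inflating the sample size would also restore power. This stands as a limit on magnitude. Inflation would not settle how the subjects are counted, though, and it uses patients that moving one calendar mark would save.

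A reader might infer several stronger things that the documents do not support:

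- **Bias between arms.** Cancellation before any capsule, with assignment blinded (Protocol 4.0), gives no evident route to a difference between arms. Uneven numbers within blocks do not invalidate Fisher's test.
- **That imputation causes the power loss.** The loss comes from missing subjects; a no-imputation rule alone would not raise the powers above.
- **That every changed or postponed operation is affected.** Such a patient can still be drilled, dosed and tested, and is then observed. Only a subject without a valid audiogram is imputed.
- **That these patients would count as PTS-negative.** No section says so.
- **That eligibility is checked only at baseline.** Protocol 10.0 lists the eligibility form as due both at consent and before surgery, and Protocol 5.3 describes a preoperative workup with laboratory and pregnancy tests. What remains is that ineligibility found then comes after randomisation, so the subject is already in the ITT sample.

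Finally, 33 days is the edge of the window, and Protocol 5.2 itself fixes no randomisation day.

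**Conclusion.** The point holds for subjects whose operation is cancelled after randomisation and who therefore have no drilling, no dose and no valid 30-day audiogram. Under the SAP they stay in ITT and are imputed; under Protocol 6.0 and the estimand's population they do not belong. It would be wrong to read the documents as having settled on imputation: they contradict each other, and that contradiction is the firm part of the finding.

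The size rests on an assumed cancellation rate: a loss of about 1.5 points of power at 2%, 3 at 5%, 5 at 10% and 9 at 15%, from 80.7%. Protocol 12.3 expects no losses, while the missing-data sections allow for under 5%. The damage is to precision and interpretability. This is a cheap improvement that should be made, and the trial's validity does not depend on it.

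**What to change.** 1. **Protocol 9.0 and SAP 2.6:** move the randomisation mark to the surgery column. The interactive randomisation tool assigns the kit number at kit release, once surgery is confirmed to go ahead and the pre-surgery eligibility form is complete. The questionnaire stratum is still recorded at baseline.
2. **SAP 4.2 and 5.2, together:** state that subjects randomised but neither dosed nor operated on are not imputed in the primary analysis and are reported by arm. Both sections must change, because a no-imputation rule in 5.2 alone would leave these subjects in an ITT sample with no outcome. Limiting the rule to cancellations before the first capsule keeps it unrelated to treatment.
3. **Reconcile** Protocol 6.0 and 12.1 with SAP 3.1, 4.2 and 5.2, and start the estimand's 30 days at surgery, as the endpoint does.

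**Cost.** One mark in each calendar, a change to when the randomisation tool is used, and aligned wording. The downside is a transaction on the day of surgery, when kits are handed over anyway. The documents do not say how much notice the pharmacist needs, so that should be confirmed.

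**What it does not solve.** Subjects whose drilling proves shorter than planned would still be randomised and stay in the analysis. If enrolment is too far advanced for step 1, steps 2 and 3 can still be adopted before unblinding.
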